1. BACKGROUND AND HYPOTHESIS

1.1. Physical Activity in Hispanic Women Population

In the last decade, regular physical activity (PA), particularly exercise, has been shown to play an important role in improving the disease course of many chronic neurological conditions, such as Parkinson's disease, Multiple Sclerosis, and headache. Unfortunately, the generalizability of these findings to other diverse populations is unclear since the vast majority of clinical research has been conducted in non-Hispanic men with affordable access to medical care. In addition, studies examining the population of people regularly engaged in physical activity in this country have indicated that lack of physical activity is particularly prevalent in Hispanic groups compared to non-Hispanic white individuals. In terms of gender, a significantly high percentage (74%) of Hispanic women do not participate in exercise activities and this number climbs with age. While there a number of reasons for this occurrence, a significant contributor includes lack of resources and accessibility to programs that promote PA and exercise.

1.2. Role of Physical Activity in Chronic Neurological Disorders

Neurological disorders, including stroke, headache, Parkinson's disease (PD) and multiple sclerosis represent the most common cause of disability world-wide⁷. While there are treatments available for many disorders, these medications often provide modest relief and are expensive with limited accessibility to this population we serve. There also remain no effective cures. In the last decade, published studies have supported the vital role of PA (particularly exercise) in many chronic neurological disorders by improving neurological outcomes, quality of life, and potentially modifying disease course^{1,8}. A limitation is that the majority of studies have been conducted in non-Hispanic white populations. In addition, PA is known to be significantly lacking in the Hispanic population overall, particularly in Hispanic women. This application will begin to address this gap by examining the role of coaching and wearable devices in promoting PA in Hispanic women population with chronic neurological conditions.

1.3. The Wellness Center at the Historic General Hospital

The Wellness Center at the Historic General Hospital (TWC) located next to Los Angeles County/University of Southern California (LAC +USC) medical center, serves a large and diverse ethnic population, many of whom are Hispanic and live within close proximity to LAC+USC hospital. TWC serves as a community center and is also a referral for patients seen at the LAC/USC Outpatient Neurology Clinics. TWC offers an opportunity to engage this diverse ethnic population of patients in an educational exercise program, along with coaching and social support, factors that have been shown to promote behavioral change.

1.4. Hypothesis

The primary goal of this proposal is to demonstrate the feasibility of using a Fitbit charge to monitor and promote physical activity in a diverse population of Hispanic women with chronic neurological disorders. Hispanic women will also receive behavioral coaching using a Lifestyle Redesign approach (see below) to enhance physical activity in their daily lives. The secondary goal of this proposal is to investigate whether changes in physical activity are associated with (i) quality of life including perception of health and well- being and (ii)

frequency of hospital and county clinic visits.

2. OBJECTIVES AND PURPOSE

2.1 Primary Objective

This pilot study will provide feasibility on use of wearable technology for tracking and selfmonitoring PA as well as preliminary data to support our overall approach for promoting PA and improving disease status in a Hispanic women population. A larger application will be submitted to the NIH, DoD, or other federal agency focused on investigating the impact of PA on chronic neurological diseases in a diverse and inclusive Hispanic population in LA County.

2.1.1 Specific Aim 1

Specific Aim 1 establishes feasibility of this approach by measuring adherence and change in PA using a Fitbit Alta HR activity monitor in Hispanic women with chronic neurological diseases. Adherence will be determined through: (i) the average hours/day of use; and (ii) the length of time (percent of total study days) of usage throughout the 16-week study. Adherence defined as (i) 5 or more days/week of use and (ii) 10 or more hours of use during the day.

2.1.2 Specific Aim 2

Specific Aim 2 tests the hypothesis that an increase in physical activity will be correlated with a decrease in LA County (LAC) Facilities health care use (hospital and clinic visits). Physical activity will be assessed by change in either: (i) the average number of steps/week; and (ii) average time spent in sedentary, light, or moderate to vigorous intensity based on MET (metabolic expenditure) of physical activity/week. Methods: Changes in PA outcome metrics over the 16-week period will be correlated with the total number of hospital/outpatient clinic visits. Total hospital use will be determined through the LAC/DHS (Department of Human Services) electronic medical records and will include outpatient provider visits, emergency room and urgent care visits, total hospitalizations, and days spent in hospital.

2.1.3 Specific Aim 3

Specific Aim 3a tests the hypothesis that increase in physical activity is associated with an increase in the quality of life (QOL). Physical activity will be measured through: (i) the average number of steps/week; and (ii) average intensity of physical activity/week. QOL will be determined through measures of self-rated health and well-being. These Spanish validated surveys will include illness perception questionnaire and health and well-being questionnaire

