3.0 STUDY DESIGN

3.1 Overall Study Design

This is a 16-week single group study of PA promotion and monitoring along with its effect

on Neurological Health. Twenty Hispanic women seen at LAC/USC Neurology clinic will be referred to TWC and invited to participate in a physical activity (PA) study for 16 weeks. Participants will receive individualized Fitbit Charge activity monitors at baseline and instructed on its usage and maintenance. Adherence to activity monitor use and amount and level of PA will be determined. All assessments that include quality of life, exercise behaviors, and self-rated health and mood will be made at baseline and at 16 weeks at TWC. Educational/coaching will take place through (i) individualized instruction on exercise at baseline and at the end of week 4 at TWC and (ii) weekly calls from TWC to promote PA goal setting as well as Fitbit use. At the end of week 1, participants will be asked to return to the TWC to review instructions on Fitbit App use and to receive further education on the benefits of exercise through a brief Power Point presentation. Patient may also receive text messages throughout the study to remind them of upcoming appointments or deadlines. General Neurological Health status will be determined through use of Electronic medical records to determine hospital and outpatient clinic visits through the 16 weeks. At study completion, participants will be allowed to keep their Fitbit activity monitor and will receive a 3-month follow up post-study call to assess the continued usage of the Fitbit charge activity monitor and a quality of life questionnaire.

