3.6.3 Determination of LA County Facilities Health Care Use

We will utilize electronic medical record (EMR) system of LA County Department of Health Services (DHS) to determine the number of hospital visits including Emergency room and urgent care visits, outpatient clinic visits, hospital stays and days within the hospital. HIPPA guidelines will be followed.

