8.0 STATISTICAL CONSIDERATIONS

8.1 Statistical Methods

Preliminary analyses will begin with an examination of the distribution of key variables to assess their characteristics (means, standard deviations, skewness, and kurtosis), to provide descriptive statistics of the study population. Continuous measures will be tested for normality and homogeneity of variance. Non-normally distributed variables will be transformed to meet the normal distribution assumption for linear statistical models.

8.1.1 Specific Aim 1

The percent of valid days of FitBit use and length of time will be calculated. We will then examine the percentage of participants who had acceptable adherence as defined as over 5 or more days/week of valid use and 10 or more hours/day length of time.

8.1.2 Specific Aim 2

Given the small sample size power to detect significant associations between physical activity and number of hospital visits will be low. Therefore, these analyses will purely exploratory. We will generate change scores from baseline to 16 weeks for both physical activity variables by subtracting week 16 scores from baseline scores. We will use Poisson regression analyses to examine the associations between changes in physical activity with our dependent variable hospital visit outcomes. Poisson regressions will be fit to account for the fact that our dependent variable (hospital visits) is a count variable and non-normally distributed. All regression models will adjust for baseline level of physical activity. Significance level will be set at 0.05.

8.1.3 Specific Aim 3

All analyses described for aim 3 are also exploratory in nature as the proposed analyses will be underpowered to detect a significant association. Change scores in Quality of life, symptoms of anxiety and depression will be calculated by subtracting week 16 scores from baseline scores. Linear regression analyses will be run examining the associations between change in PA and our dependent variable of change.

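### Aim 2 hypothesises a fall in health care use, but the 8.1.2 model has no prior-use term and can show only an association with the level of use during the 16 weeks

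*Combined protocol and SAP*

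**What the plan says.** The Aim 2 hypothesis in section 2.1.2 concerns a change in use: "an increase in physical activity will be correlated with a decrease in LA County (LAC) Facilities health care use". The Methods sentence in the same paragraph concerns a total: "Changes in PA outcome metrics over the 16-week period will be correlated with the total number of hospital/outpatient clinic visits". Use covers "outpatient provider visits, emergency room and urgent care visits, total hospitalizations, and days spent in hospital".

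Section 3.1 sets the counting period through "use of Electronic medical records to determine hospital and outpatient clinic visits through the 16 weeks". Section 3.6.3 describes the record extraction and names no pre-study period.

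Section 8.1.2 forms change scores for the PA variables only. It then states: "We will use Poisson regression analyses to examine the associations between changes in physical activity with our dependent variable hospital visit outcomes". On covariates it says: "All regression models will adjust for baseline level of physical activity". It also concedes low power and calls the analyses exploratory.

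Two other places bear on the point. Section 3.6.1 lists recent frequency of health care visits among the baseline data, without a look-back period. Section 8.1.3 does difference its outcome for Aim 3: "Linear regression analyses will be run examining the associations between change in PA and our dependent variable of change".

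**The concern.** A decrease is a comparison of a woman's use during the study with her own earlier use. The planned model holds no earlier use, whether as covariate, offset, paired count or change score. It compares women with each other: do those who gained more activity have fewer visits in these 16 weeks? A ratio below 1 could arise because visits fell in women who became more active. It could also arise because women who always use less care were the ones who became more active.

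Section 2.1 says the pilot will supply preliminary data for a larger application. There, a ratio below 1 could be quoted as the hypothesised decrease although nobody's use had changed.

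**Working it through.** **No figure to reproduce.** The plan gives no visit rate, effect size or power for Aim 2. The mismatch itself is a matter of reading and needs no simulation. The numbers below only illustrate what it could do.

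**Step 1. The texts side by side.**

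| Place | Quantity |
|---|---|
| 2.1.2, hypothesis | Decrease in use |
| 2.1.2, Methods sentence | Total visits |
| 1.4, secondary goal | Frequency of visits |
| 3.1 | Visits during the 16 weeks |
| 8.1.2 | Visit count, given PA change and baseline PA |
| 8.1.3 (Aim 3, for contrast) | Change in the outcome |

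Only the hypothesis speaks of a decrease. Every other Aim 2 text describes a level.

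**Step 2. What the coefficient estimates.** The model is log(expected visits) = a + b × PA gain + c × baseline PA. So exp(b) compares two women with equal baseline PA and different gains. Gain is signed here as week 16 minus baseline; the subtraction as worded in 8.1.2 runs the other way and would invert the ratio.

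Suppose nobody's use changes. Let usual rates be log-normal with log-scale SD s, and let r be the correlation of log rate with PA gain that remains after baseline PA (baseline PA taken as independent of both). Then the planned rate ratio per SD of gain is exp(s × r). It is exactly 1 when r = 0.

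For mean m and variance-to-mean ratio D, s² = ln(1 + (D − 1)/m). With m = 3 and r = -0.3, all assumed:

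- D = 1.25: s² = ln(1.083) = 0.080, s = 0.283, ratio exp(-0.085) = 0.92
- D = 2: s² = ln(1.333) = 0.288, s = 0.536, ratio exp(-0.161) = 0.85
- D = 3: s² = ln(1.667) = 0.511, s = 0.715, ratio exp(-0.214) = 0.81

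With r = +0.3 and D = 3 the ratio is exp(0.214) = 1.24, so the error can go either way.

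**Step 3. Simulation with 20 women.** Gamma-Poisson counts, m = 3, D = 3; median rate ratios per SD of gain. The prior count enters as log(count + 0.5).

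| Assumed truth | 8.1.2 as planned | With 52-week prior count |
|---|---|---|
| Real 21% fall per SD, r = 0 | 0.79 | 0.79 |
| No change, r = -0.3, stable rates | 0.80 | 0.97 |
| No change, r = -0.3, rates correlated 0.7 between windows | 0.79 | 0.89 to 0.90 |
| No change, r = -0.5, rates correlated 0.7 between windows | 0.68 | 0.81 to 0.84 |

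The planned model gives nearly the same answer in the first two rows. The share of the bias left after adjustment, on the log scale, is:

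- stable rates: ln 0.97 / ln 0.80 = 0.030/0.223 = 14%
- rates correlated 0.7, r = -0.3: ln 0.90 / ln 0.79 = 0.105/0.236 = 45%
- rates correlated 0.7, r = -0.5: ln 0.81 / ln 0.68 = 0.211/0.386 = 55%

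**Step 4. The condition for bias.** The raw correlation between use and gain is not what counts. A raw correlation of -0.3 that runs wholly through baseline PA (-0.5 with use, +0.6 with gain) gives 1.00. A raw correlation of zero, with baseline PA correlated -0.5 with use and -0.4 with gain, gives 0.83.

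**Step 5. One study.** With stable rates and the 52-week count, the 5th to 95th percentiles of the adjusted ratio are 0.59 to 1.05 for the real fall and 0.70 to 1.33 for no change. They overlap heavily.

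**Step 6. Secondary point: standard errors.** With no association and m = 3, plain Poisson tests at 0.05 reject in 8%, 15% and 25% of runs at D = 1.25, 2 and 3. Dispersion-scaled errors with a t reference reject in 5% to 6%.

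**The case against.** The strongest reply is that this is mostly wording. The paragraph that speaks of a decrease also says that total visits will be used; sections 1.4, 3.1 and 8.1.2 agree; and a correlation with a decrease can be read loosely as an inverse correlation. That stands in large part. It limits the defect to one hypothesis, and rewording must be part of any remedy. It does not remove the mismatch, because 8.1.3 shows that the authors specify a change outcome when they intend one.

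A second reply is that the analysis is exploratory and low-powered. That also stands and sets the severity. Exploratory status excuses imprecision; it does not make a level into a change.

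Three stronger readings are tempting and are not supported:

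- A reader might infer that the planned coefficient is biased. That needs a residual relation between habitual use and PA gain, and the documents give neither its size nor its sign.
- A reader might infer that adjusting for prior use would let the study demonstrate a decrease. Steps 3 and 5 show otherwise: about half the bias can remain, and 20 women would usually not separate a true fall from no change. PA change and visits also share the same 16 weeks, so direction stays open.
- A reader might infer that prior use is ignored altogether. Section 3.6.1 collects it, and the descriptive statistics opening section 8.1 could include it. What can be said is that the Aim 2 model does not name it.

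**Conclusion.** The point holds, as a minor one. The 8.1.2 model addresses whether PA change is associated with the level of visits during the 16 weeks. It does not address the decrease hypothesised in 2.1.2. Confidence in that mismatch is high, because it rests on the text alone.

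The size of any bias is unknown. The illustrative ratios rest on assumed visit rates, spread between women, residual correlation and stability of use over time, none of which the documents give. If the residual correlation is zero there is no bias from this source.

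The consequence is limited: no decision rule uses the coefficient, and the feasibility question of Aim 1 is unaffected. The standard-error point is separate and adds nothing to the severity.

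**What to change.** 1. **In all cases, reword the Aim 2 hypothesis in 2.1.2** to match the estimate: an association of PA change with visits during the 16 weeks, given prior use if that is available, and otherwise with the level of use.
2. **If the record and the authorization cover it, add prior use to the total-visit model in 8.1.2.** Extract the same visit types from the same county record over a defined pre-baseline window and enter log(prior count + 0.5), keeping baseline PA. A 52-week window leaves less residual bias than a 16-week one. Section 4.1 requires clinic visits spanning more than a year, so an earlier record should exist, but the documents do not confirm that the record or authorization reaches back that far.
3. **Secondary:** use dispersion-scaled errors with a t reference, and report sparse outcomes (hospitalizations, hospital days, any count below about one per woman) descriptively. At an assumed mean of 0.2 events per woman, the model with the prior count could not be fitted in 16% to 34% of runs.

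**Cost.** One more date range in an extraction already planned, a few sentences, and no extra patients or visits. With one PA change term per model, residual degrees of freedom go from 20 − 3 = 17 to 20 − 4 = 16. In the simulations for total visits (m = 3, true ratio 0.79, scaled errors), power without and with the 52-week count was 30% and 31%, 22% and 29%, and 16% and 26% at D = 1.25, 2 and 3, so the covariate cost no power there. If no look-back is available, items 1 and 3 need only text changes.

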3.6.2 Physical Activity, Adherence Assessment

Data gathered from Fitbit based device will be stored, visualized and aggregated through a commercially available service (Fitabase Inc, Https://www.Fitabase.com). Fitabase is a research friendly application

programming interface that allows the device data from all users to be identified through a uniquely assigned ID# and transmitted in a secure fashion to the data acquisition and integration center. Data is downloaded from Fitabase in a de-identified matter and is ready for statistical analysis (i.e. CSV files that are SPSS ready). The Fitabase one-time set-up process (taking approximately five minutes) will take place at the wellness center to establish a continuous, passive and secure data stream of all measures. The following measures will be obtained during the course of the study: (i) step count, (ii) time spent in sedentary, light, moderate, and vigorous activity, and (iii) length of wear.

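### Aims 2 and 3 score activity per week with no wear condition, so on the natural reading a change in days worn counts as a change in activity

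*Combined protocol and SAP*

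**What the plan says.** Section 2.1.2 (Aim 2) assesses activity by "change in either: (i) the average number of steps/week; and (ii) average time spent in sedentary, light, or moderate to vigorous intensity", on a weekly basis. Section 2.1.3 (Aim 3) states: "Physical activity will be measured through: (i) the average number of steps/week; and (ii) average intensity of physical activity/week".

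Section 8.1.2 says "We will generate change scores from baseline to 16 weeks for both physical activity variables" and "All regression models will adjust for baseline level of physical activity". Section 8.1.3 regresses change in the outcome on change in activity. Neither section names a valid-day rule, a scaling to wear time, a wear covariate, or the weeks that make up the baseline and week-16 values.

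A wear rule exists only for Aim 1, in 2.1.1 and in 8.1.1, where the analysis reports the percentage of women with "acceptable adherence as defined as over 5 or more days/week of valid use and 10 or more hours/day length of time". Wear is nevertheless recorded: Section 3.6.2 lists "i) step count, (ii) time spent in sedentary, light, moderate, and vigorous activity, and (iii) length of wear".

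On status, 8.1.2 says "these analyses will purely exploratory" and 8.1.3 says "All analyses described for aim 3 are also exploratory in nature".

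**The concern.** The trial treats wear as uncertain: whether women keep the device on is the Aim 1 question. Yet the activity scores in Aims 2 and 3 take no account of it. If the weekly figure is a sum, an unworn day adds no steps and no active minutes, and a woman whose habits are unchanged can show a large change score.

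Two consequences follow. Wear change unrelated to outcome adds noise to the exposure in a sample of about 20. Wear change related to outcome can create an association. If a woman wears the device less when unwell (assumed), her measured steps and active minutes fall while her visits rise and her quality of life falls. That is the hypothesised direction, with no effect of activity behind it. Section 2.1 intends the results as preliminary data for a larger federal application, so a wear artefact could be carried forward as a signal.

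**Working it through.** The plan gives no numerical figure on this point to reproduce. Percentages below are week 16 relative to baseline.

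**1. Exact arithmetic.** Weekly total = days worn × steps per worn day. With steps per worn day constant:
- 7 to 5 days: 5/7 − 1 = −28.6%
- 5 to 7 days: 7/5 − 1 = +40%

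With at least 10 hours on each worn day, weeks of 5, 6 and 7 days all meet the Aim 1 definition, so full adherence does not remove the effect. With 7 to 5 days, a true rise of 40% per day is needed to break even. The same arithmetic applies to active minutes spread evenly over days. Aim 3's average intensity is not a total and is less affected.

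**2. Noise (illustrative).** Assumed inputs, none from the plan: 6,000 steps/day at baseline (between-woman SD 2,000), true change +500/day (SD 1,500), wear equally likely to be 5, 6 or 7 days and independent between weeks, unworn days as active as worn days.

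| Window | Correlation of measured with true change | True increasers scored as decreasing |
|---|---|---|
| Single weeks | 0.76 | 19% |
| 4-week averages | 0.92 | 10% |

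If every woman wears the device 7 days at baseline and a mean of 6 days at week 16, the true mean change is 7 × 500 = +3,500 steps/week. The measured mean is 6 × 6,500 − 7 × 6,000 = −3,000. Averaging over 4 weeks does not remove that shift.

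**3. False positives (illustrative).** Same inputs, n = 20, linear model as in Aim 3, adjusted for baseline activity, two-sided 0.05, no true activity effect. The correlation of worn-day change with outcome is assumed. Repeat runs differ by about one percentage point.

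| Activity measure | Correlation 0 | 0.3 | 0.5 |
|---|---|---|---|
| Weekly total, single weeks | 5% | 11% | 22% |
| Weekly total, 4-week averages | 5% | 7% | 12% |
| Mean per valid day | 5% | 5% | 5% |

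The size therefore depends heavily on the averaging window, which the plan leaves open.

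**4. Hours within a valid day.** A per-day mean does not remove these: 14 to 10 hours is 10/14 − 1 = −28.6% if steps accrue evenly over wear. If change in hours (10 to 14 per day, assumed) correlates 0.3 or 0.5 with outcome, the per-valid-day mean gives 9% or 16% false positives. Adjusting for change in hours restores 5%.

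**5. The assumption that favours the per-day mean.** Step 2 takes unworn days to be as active as worn ones. Relaxing this for single weeks gives the following correlations with true weekly change:

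| Activity on unworn days, relative to worn days | Weekly total | Per valid day |
|---|---|---|
| 100% | 0.76 | 1.00 |
| 75% | 0.87 | 0.98 |
| 50% | 0.95 | 0.93 |
| 25% | 0.99 | 0.85 |

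Below about half, the weekly total tracks true change better.

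**6. Scores lost to a valid-day minimum.** Assume 80% or 90% of days are valid, days independent, one week at each end. P(at least 5 of 7) = 0.852 or 0.974; squared × 20 = 14.5 or 19.0 women. P(at least 4 of 7) = 0.967 or 0.997, giving 18.7 or 19.9.

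**The case against.** The strongest reply is that both aims are declared exploratory and underpowered, so no decision rests on them. That stands and limits the consequence. But 8.1.2 still sets a 0.05 level, and low power does not protect against bias.

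Second, the plan never uses the word total. A mean over worn days, reported weekly, is not excluded. That also stands: a reader might infer that the plan prescribes a sum, and it does not say so. If another quantity was meant, the measure is undefined and the same repair is needed.

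Third, a reader might infer that falling wear always biases towards the hypothesis. The documents do not support this for sedentary time. If unworn hours add nothing, sedentary time falls in a woman who is doing worse, which works against the hypothesis. If unworn hours are coded as sedentary, the direction reverses. The coding is not stated.

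Fourth, wear is supported in practice: Section 3.4 asks for daily wear and follows it by weekly calls and data monitoring. This may keep the effect small, but it does not define the score. The self-report activity questionnaire in 3.7.5 does not depend on wear, but it is not named as the Aim 2 or Aim 3 activity measure.

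Finally, a per-valid-day mean is not better under every assumption, as step 5 of the working shows, and a valid-day minimum may preferentially drop the less well women. Both points stand and shape the fix.

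**Conclusion.** The concern holds for steps per week in Aims 2 and 3 and for weekly time in intensity bands in Aim 2, on the natural reading of the weekly average as a sum. The exact part is −28.6% for 7 to 5 worn days and +40% for 5 to 7, at constant daily activity. The noise and false-positive figures are illustrations from assumed inputs. They range from negligible to substantial according to the window and to how closely wear follows health, which the documents do not tell us. The direction argument covers steps and active minutes only, and rests on the assumption that wear falls with illness. No decision rule changes. This should be corrected because the associations and the preliminary data cannot be read clearly without it, and because with 20 women a wear rule chosen after seeing the data would be an avoidable freedom.

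**What to change.** In 2.1.2, 2.1.3 and 8.1:
- Define activity as mean steps and mean active minutes per valid day, using the plan's own 10-hour threshold, with sedentary time as a share of wear time.
- State which weeks form the baseline and week-16 values, and one minimum number of valid days.
- Report valid days and wear hours at both times.
- Add one sensitivity analysis adjusting for change in wear hours, and keep the weekly total as a comparison, since it may do better if unworn days are much less active.

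The cost is wording in the objectives and the statistical section. Length of wear is already collected, and eligibility and visits are unchanged. The price is lost change scores: under the assumptions in step 6, a 5-day minimum at both ends keeps about 14.5 to 19.0 of 20 women, and a 4-day minimum about 18.7 to 19.9. Those lost may be the less well women, so the report should describe them.

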6.0 CLINICAL EVALUATIONS AND STUDY CALENDAR

Parameter	Screening Visit	Baseline Visit	Weeks 1-4	Week 4	Weeks 5-16	Week 16	Week 28
Demographic Information		Х					
Lifestyle Redesign Coaching		Х		Х			
Fitbit Charge Activity Monitor Instruction		Х					
Quality of Life (QOL)		Х				Х	
Spanish Acculturation		Х					
Brief Illness Perception Questionnaire (BIPQ)		Х				Х	
Patient Activation (PAM)		Х				Х	
Physical Activity Questionnaire		Х				Х	
FitBit Wear Technology Questionnaire						Х	
Phone Call for FitBit Use		Х	Х	Х	Х	Х	
Post-Study Phone Call on FitBit Use							Х

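### Aim 2 counts visits over the same 16 weeks that define the activity change, so an illness lasting to week 16 can produce the hypothesised association with no effect of activity

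*Combined protocol and SAP*

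**What the plan says.** Aim 2 (Section 2.1.2) sets out the hypothesis that "an increase in physical activity will be correlated with a decrease in LA County (LAC) Facilities health care use". Its method sentence reads "Changes in PA outcome metrics over the 16-week period will be correlated with the total number of hospital/outpatient clinic visits". That sentence does not date the visits. Section 3.1 does, by using "Electronic medical records to determine hospital and outpatient clinic visits through the 16 weeks".

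Section 8.1.2 builds the predictor from two time points: "We will generate change scores from baseline to 16 weeks for both physical activity variables by subtracting week 16 scores from baseline scores". The model follows: "We will use Poisson regression analyses to examine the associations between changes in physical activity with our dependent variable hospital visit outcomes". The only covariate is given by "All regression models will adjust for baseline level of physical activity". The significance level is 0.05, and the analysis is called exploratory because power is low.

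The documents specify no lag between activity and visits, no later record window and no sensitivity analysis for illness during the study. Section 3.6.1 collects each woman's recent frequency of health care visits at baseline, but the Aim 2 model does not use it. The calendar in Section 6.0 already contains a week 28 contact ("Post-Study Phone Call on FitBit Use").

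**The concern.** The predictor is complete only at week 16, while the outcome accumulates from the start of the study. A visit in week 10 cannot result from activity measured in week 16, but the illness behind that visit can still depress week 16 activity. Such an illness raises the outcome and lowers the predictor. The resulting association runs in the hypothesised direction, and adjustment for baseline PA does not touch it because the illness arises after baseline.

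The participants have chronic neurological disorders, so illness lasting for weeks is plausible. Section 2.1 describes the pilot as a source of preliminary data for a larger federal application. If the same timing were kept there, the bias would be kept too, because it does not shrink with sample size.

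**Working it through.** The plan gives no visit rate, effect size or power for Aim 2, so there is no figure of its own to reproduce. Everything below on illness and visit rates is an assumption, shown as a range.

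**Inputs from the documents:** 20 women in a single group; visits counted in weeks 1-16; change score from baseline to week 16; Poisson regression adjusted for baseline PA; significance level 0.05 (taken as two-sided).

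**Assumed:** visits are Poisson with mean 3.5, plus 3 if ill; a fraction p of women is ill (10-30%); PA change has SD 1 in women without illness and is lowered by d SD if ill (0.5-1.5). PA has no effect on visits.

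**Step 1, hand approximation.** With baseline PA unrelated to illness:
- covariance of PA change and visits = -d × p(1-p) × 3
- mean visits = 3.5 + 3p
- variance of PA change = 1 + d² × p(1-p)
- log rate ratio per SD increase in PA ≈ covariance / (mean × variance)

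Mild end (p = 0.1, d = 0.5): -0.5 × 0.09 × 3 = -0.135; mean 3.8; variance 1.0225; -0.135 / (3.8 × 1.0225) = -0.035; rate ratio 0.97.

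Strong end (p = 0.3, d = 1.5): -1.5 × 0.21 × 3 = -0.945; mean 4.4; variance 1.4725; -0.945 / (4.4 × 1.4725) = -0.146; rate ratio 0.86.

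Sample size does not enter the formula.

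**Step 2, simulation of the planned model at n = 20, no true effect.**

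| Scenario | Rate ratio per SD increase in PA | Rejection at nominal 5%, Poisson errors |
|---|---|---|
| Weeks 1-16 visits; illness leaves week 16 PA unchanged | about 1.00 | 6-11% |
| Weeks 1-16 visits; illness lowers PA change by 0.5-1.5 SD | 0.86-0.96 | 10-37% |
| Later 12-week window, illness resolved | about 1.00 | 4-6% |
| Later window, one third of the illness effect persists | 0.93-0.98 | 6-11% |
| Later window, illness fully persists | 0.87-0.97 | 14-29% for 20-30% ill and a 1-1.5 SD drop |

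The first row isolates Poisson overdispersion: illness makes visit counts more variable than the model allows, whatever the timing. With overdispersion-scaled errors the second row becomes 8-29%. Repeat runs at the mild end gave a rate ratio of 0.97 with 8-9% unscaled rejection, and 5-8% scaled for a 0.5 SD drop. At that end the excess in rejection is hardly separable from overdispersion.

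**Step 3, the same check in steps per day.** Assumed: mean 2 visits without illness, PA change +1 (SD 1.5) thousand steps/day, 20% of women ill. Rate ratio per +1,000 steps/day:
- illness doubles visits and takes 1,000 steps/day off week 16 activity in half of those ill: 0.97
- illness triples visits and takes off 2,000 in all of those ill: 0.855
- illness triples visits but week 16 activity has recovered: 1.00

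With 1,000 women the first two ratios are unchanged at 0.97 and 0.855.

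**Sign.** Section 8.1.2, read literally, computes baseline minus week 16, so an increase in PA is a negative score and the hypothesised coefficient is positive. The ratios above are per *increase* in PA. Under the literal coding they invert, to 1/0.96 = 1.04 and 1/0.86 = 1.16.

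**The case against.** The strongest reply is that Aim 2 belongs to the secondary goal, is worded as correlation, and is labelled exploratory in Section 8.1.2. Uncertain direction is a limitation of any observational association in one group of 20. This stands as a limit on the consequence. It does not answer the point, because the stated reason for the label is low power, a 0.05 test is kept, and the timing problem is nowhere mentioned.

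The reply is also right on several stronger readings that a reader might infer:

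- *That the overlap of windows by itself creates the association.* It does not. The illness must still depress activity when week 16 is measured; one that has resolved leaves the rate ratio at about 1.00. Eligibility also requires unassisted walking and excludes conditions that preclude exercise, which may keep the illness fraction low.
- *That hospital days cut the activity score mechanically.* If the week 16 score were one week's average and three inpatient days counted as near zero, the cut would be about 3/7 = 43%. The plan does not say how inpatient or unworn days enter the average, and averaging over worn days could remove that cut.
- *That the whole excess in false positives is due to timing.* Part of it is overdispersion, as the first table row shows.
- *That a later window settles direction.* It does so only if the illness has resolved, which cannot be taken for granted in chronic disease.
- *That the coefficient will be presented as a causal effect in the larger application.* The documents do not say so.

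**Conclusion.** The concern holds in a limited form. As planned, an illness that both adds visits and persists to week 16 can produce the hypothesised association with no effect of PA. Under the assumed ranges the apparent rate ratio is about 0.86-0.96 per SD increase in PA, with rejection of about 10-37% unscaled and 8-29% with scaled errors. These sizes rest on illness and visit rates that the documents do not supply, and the mild end is close to nominal. The documents do not support saying that an observed association would be wholly due to illness, or that Aim 2 is invalid. This is a worthwhile, inexpensive improvement to an exploratory analysis.

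**What to change.** Keep the planned weeks 1-16 model and add to Section 8.1.2:

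1. A sensitivity analysis that extends the same record query to week 28 and fits the same model to visits in weeks 17-28. Add the baseline visit frequency already collected under Section 3.6.1 as a covariate where event numbers allow.
2. A statement that the weeks 1-16 association cannot show direction, and that the lagged model is less biased but not causal if illness persists.
3. The hypothesised direction in words (fewer visits with increased PA), together with the coding of the change score, so that the sign of the coefficient cannot be misread.

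The cost is a longer query and authorization wording that reaches week 28; no extra visit is needed. The lagged model will be less precise. At the assumed 3.5 visits per woman in 16 weeks, expected visits fall from 20 × 3.5 = 70 to 70 × 12/16 = 52.5, which widens standard errors by a factor of about √(16/12) = 1.15.
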